## **VII. RISKS AND DISCOMFORTS**

Complications from Surgical and Non-Surgical Procedures : Not applicable to this study. There are no surgical and non-surgical procedures.

- a. Although all patients are eligible for open-label Entresto at randomization, those randomized to group B will be initiated 6 weeks later than those in group A. This may delay access to the potential incremental benefits of Entresto; however, there is currently a wide variation of practice in initiation of Entresto. This is partly related to cost and partly to concern for how best to titrate this agent in the setting of diuretics and beta blocking agents that the patient will continue to take.

### **b. Drug Side Effects and Toxicities**

Subjects are not exposed to any risks other than those occurring during standard approved care for HFrEF, which includes both the medication Entresto and the CardioMEMS monitoring device. The only way in which their enrollment in the study differs from standard of care is that they will undergo more frequent monitoring, which increases the safety of drug titration to avoid lowering of filling pressures to levels that might be associated with postural hypotension when Entresto is added to their previous HF regimen.

It is unlikely that there will be any adverse effects of holding ACEI/ARB for 2 days (minimum 36 hours as per FDA labelling) at the beginning of the study. For the A group, this would occur anyway for safety, as a washout period of at least 2 days (minimum 36 hours as per FDA labelling) is required before initiation of Entresto. For the B group who will resume ACEI/ARB after 2 days (minimum 36 hours as per FDA labelling), such pauses in one component of therapy

are common around the time of surgery and are not anticipated to lead to any symptoms, as the other medications will be continued as usual.

*Common:* Based on Novartis' published prescribing guidelines for Entresto and previous clinical trials, the major side effects are similar to ACEi/ARB therapy: hypotension, hyperkalemia and renal dysfunction. All of these potential side effects will all be monitored for by study staff with frequent lab work, as is standard of care. In addition, due to their enrollment in this trial, hemodynamic assessment (including blood pressure) will be checked at each visit and PA pressures will be monitored daily by patient and reviewed by the study staff. This will increase the patient's level of safety as compared to standard clinical practice. Any dose changes will be followed by "acute PAP measurements" the next day and safety lab work as clinically indicated.

*Uncommon:* Similar to ACEi therapy, Entresto has a small risk of angioedema (0.2% in the Entresto group compared to 0.1% in the Enalapril group in the PARADIGM trial). These events have to date not been known to cause airway compromise.

To eliminate any increased risk of angioedema from prior ACEi exposure in this study, all patients will undergo a mandatory 2 day (minimum 36 hours as per FDA labelling) washout period between any ACEi administration and any Entresto administration. This is consistent with prior clinical trials as well as the standard of care and for any patient switching from ACEi to Entresto, regardless of whether or not they were enrolled in this study.

If a patient has an adverse reaction to any drug in the study (ACEi, ARB or Entresto) that cannot be ameliorated with dose reduction or adjustment, the medication will be stopped. No patients will be "removed" from the study. Even if a patient experiences symptoms that require cessation of the medication, we will continue to monitor them for the duration of the study.

### **c. Device Complications/Malfunctions**

Subjects are not exposed to any risks from their monitoring device other than those consistent with the standard of care for HFREF. All of the patients enrolled in this study already have CardioMEMS devices in place for clinical indications. Therefore, they incur no additional risk from the CardioMEMS device by enrolling in this study. There is essentially no risk from making pressure measurements and transmitting them to a central server.

### **d. Psychological (Non-Medical) Risks**

*Common:* There are no expected, common psychological risks to the patients in this study. Patients undergoing pulmonary pressure monitoring at home generally feel reassured by regular transmission of data to a health care team. Monitoring in this study will be even more frequent and intensive than normal care, which may be even more reassuring to the patient. *Uncommon:* There are no expected, uncommon psychological risks to the patient from participation in this

study. If a patient experiences any new psychological symptoms during the course of this study, he/she will be referred, as per standard care, to the appropriate psychological and/or psychiatric resources.

#### **e. Radiation Risks**

This is not applicable to this study since patients are not exposed to radiation during this study. No statement from the Radiation Safety Committee is necessary.

### **VIII. POTENTIAL BENEFITS**

#### **a. Potential Benefits to Participating Individuals**

The subjects enrolled in this study will receive Entresto at no cost. This medication decreases both HFREF mortality and hospital readmission rates.. Patients enrolled in this study will be provided with Entresto for the duration of the study (Group A 32 weeks, Group B 26 weeks). At the conclusion of the trial, subjects can discuss receiving Entresto as part of their heart failure medical therapy with their physician. It is likely that the information gained from monitoring PAP will allow earlier identification of a need for adjustment in a concomitant medication. This could lead to lower incidence of reversible side effects such as hypotension and renal dysfunction. As compensation for patient time and effort, the study will provide \$25/visit for each of the 8 required clinic visits during this study. This will cover both the cost of parking (\$10 for up to 4 hours in the BWH patient parking lot) and the cost of a meal at the hospital.

#### **b. Potential Benefits to Society**

It is hoped that this study will help the medical community to better understand what effect, if any, Entresto has on pulmonary pressures. It is hoped that this information will allow physicians to better select the right doses and to adjust other medications with Entresto for greater benefit and safety. If, as anticipated, Entresto is shown to cause a sustained decrease in PA pressures, a further trial can be designed to determine if and how it could delay or prevent the development of secondary right-sided heart failure, which often heralds irreversible decompensation for patients with reduced left ventricular ejection fraction.

### **IX. SAFETY MONITORING AND REPORTING**

#### **a. Independent Monitoring of Source Data**

Trained research assistants will be responsible for inputting the data into the locked study database. The study's project coordinator will then be responsible for verifying key baseline data within one week of enrollment for each patient enrolled. The project coordinator will also review the study data on a monthly basis thereafter for accuracy. The study database will be checked monthly using random audits of ~10% of subjects for data for missing, out-of-range, or inconsistent values.

#### **b. Safety Monitoring**

Due to the fact that we are using an FDA approved drug for its FDA approved indication and a previously-placed FDA approved device for its FDA approved indication, we will not have a formal Data Safety Monitoring Board. Nevertheless, we will take all necessary steps to ensure the safety of our patients and the validity of the results.

All of the study data will be stored on a Partners desktop computer housed in a locked office in the Advanced Heart Failure section of Building A at BWH. A dedicated and trained data entry research assistant will enter all initial demographic data within 2 days of a patient's enrollment in the study into a secure, password protected database. A study coordinator will verify the accuracy of the information on a regular basis to check for accuracy.

Subsequent clinical information obtained during the course of the study, will be entered into the password-protected database by a trained research assistant per standard protocol and a study coordinator will review the accuracy of this information as well. The investigators will review all safety and data management policies and procedures with new staff and annually with current staff.

This study will have an independent reviewer (licensed cardiologist who practices outside of the Partners System and has no involvement with or relation to the study) to review, in a de-identified fashion, any/all potential adverse events and determining if they are appropriate to report to Novartis and the Partners IRB.

#### **c. Outcome Monitoring**

This study will have an independent reviewer (licensed cardiologist who practices outside of the Partners System and has no involvement with or relation to the study) to review both results of the study. The independent reviewer for this study will be:

[name]  
Beth Israel Deaconess Medical Center.  
Director of the Ventricular Assist Device Program  
Associate Director of Advanced Heart Failure

[name] is a heart failure specialist outside the Partners system who is experienced in both the clinical care of heart failure patients and in clinical investigation, having participated in clinical

events adjudication, patient recruitment, and Data Safety Monitoring Committee roles for a number of cardiovascular device and pharmaceutical trials. He is an active clinical member of the Cardiovascular Division and the Associate Director of the Advanced Heart Failure Program at Beth Israel Deaconess Medical Center. In addition, he is currently a member of the Clinical Events Committee for the Harvard Clinical Research Institute in Boston, MA as well as a member of the Data Safety Monitoring Committee for a clinical trial of esmolol in severe sepsis.

Specifically, [name] will review all endpoint data including PA pressures (daily trends, acute/first dose/dose change PA pressures, exercise recovery PA pressures) hemodynamic and side effect information obtained in clinic, 6-minute walk test, double Master's step test, Handgrip test, Stroop Color test, laboratory work, KCCQ scores and medication dose changes. He will be blinded to the study group assignment and will review this data in a de-identified fashion. He will also be responsible for reviewing any/all potential adverse events and determining if they are appropriate to report to Novartis and the Partners IRB. He will review all clinical and safety data after every 5 patients have been enrolled. Potential adverse events will be reviewed as soon as possible if/when they occur. The study will have a pre-specified stopping guideline of  $p < 0.01$  for harm on any safety outcomes.

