## Power Analysis

There will be 20 patients total, 10 in each group.

*Between group comparison:* This sample size will provide 90% power with 2-sided alpha of 0.05 to detect a 20% difference between the 2 groups (Entresto and ACEI/ARB) in the PAPm change at 6 weeks, based on an assumed baseline PAPm of 25 mm, using a t-test with a standard deviation in the mean change of as high as 3.4. We do not yet have data on which to estimate the standard deviation of this change, but we have found a standard deviation of 3-4 mm Hg of PAPm pressures during 5 day periods in stable patients followed on Cardiomems devices at Brigham and Women's Hospital (unpublished data).

*All patients after 6 weeks of Entresto compared to chronic ACEI/ARB at baseline:* There is additional power for this highest secondary endpoint. Assuming the PAPm baseline on ACEI/ARB mean of 25mm, a sample size of 20 patients will provide 90% power with two-sided alpha of 0.05 paired t-test to detect a 20% decrease (to PAPm of 20 mm) after 6 weeks of Entresto, with a standard deviation for the change as high as 6.8.

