#### **d. Adverse Event Reporting Guidelines**

All of the following events will be collected for review by the independent reviewer and reported to Novartis Pharmaceuticals (along with the relevant randomization codes): All serious adverse events (SAE), all reports of drug exposure during pregnancy, all non-serious adverse events, all reports of misuse and abuse of the study drug, other medication errors, and uses outside what is foreseen in the protocol (irrespective of whether a clinical event has occurred). Any member of the study team can report a potential adverse event. Since Entresto is an FDA approved drug and it will be using it for its FDA approved indication, any adverse events thought to be related to Entresto will be reported FDA's MedWatch program, in keeping with standard practice. Given the mechanism of action of the drug, angioedema is an event of special interest, and all angioedema-like events will be submitted for independent review. Any adverse events that are deemed "significant" by the independent reviewer will also be reported to the Partners IRB.

An SAE is defined as any adverse event (appearance of or worsening of any pre-existing) undesirable sign(s), symptom(s) or medical conditions(s) which meets any one of the following criteria:

- is fatal or life-threatening
- results in persistent or significant disability/incapacity
- constitutes a congenital anomaly/birth defect
- requires inpatient hospitalization or prolongation of existing hospitalization, unless hospitalization is for:

- routine treatment or monitoring of the studied indication, not associated with any deterioration in condition (specify what this includes)
- elective or pre-planned treatment for a pre-existing condition that is unrelated to the indication under study and has not worsened since signing the informed consent
- treatment on an emergency outpatient basis for an event not fulfilling any of the definitions of a SAE given above and not resulting in hospital admission
- social reasons and respite care in the absence of any deterioration in the patient's general condition
- is medically significant, i.e. defined as an event that jeopardizes the patient or may require medical or surgical intervention.

All malignant neoplasms will be assessed as serious under “medically significant” if other seriousness criteria are not met.

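### The independent reviewer's only dated cumulative safety reviews follow enrolment, with no minimum follow-up and none dated after the 20th patient enters

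*Combined protocol and SAP*

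**What the plan says.** Section IX.c (Outcome Monitoring) sets the timing of the cumulative review: "He will review all clinical and safety data after every 5 patients have been enrolled". The Power Analysis fixes the sample: "There will be 20 patients total, 10 in each group". Section IX.b explains why one reviewer carries this role: "we will not have a formal Data Safety Monitoring Board".

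IX.c contains three further provisions:

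- Individual events are handled continuously: "Potential adverse events will be reviewed as soon as possible if/when they occur".
- The reviewer will look at all endpoint data (PA pressure trends, clinic hemodynamics and side effects, laboratory work, dose changes), but no date is given.
- There is a stopping guideline of p < 0.01 for harm on any safety outcome, not tied to any named look.

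Section IX.d widens the event stream to serious and non-serious events alike: "All of the following events will be collected for review by the independent reviewer and reported to Novartis Pharmaceuticals".

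On exposure, section VIII.a promises "Entresto for the duration of the study (Group A 32 weeks, Group B 26 weeks", and section VII says "those randomized to group B will be initiated 6 weeks later than those in group A". Section V.b places the first study dose on day 5 and Group B's first Entresto dose on day 47. No accrual rate or enrolment period is stated.

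**The concern.** Section VII.b names hypotension, hyperkalemia and renal dysfunction as the main side effects. These arise with exposure and up-titration, not with enrolment. A trigger that counts enrolments therefore sees less Entresto exposure the faster the trial recruits. It also stops producing reviews when the last patient enters, while laboratory, blood pressure and PA pressure data keep arriving to week 32.

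What is at stake is the aggregate view: a drift in potassium, creatinine or pressure across patients that nobody reports as an event in any one of them. A harm guideline expressed as a p-value also needs accumulated data and a defined time to look at them.

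**Working it through.** **Inputs.** 20 patients, 10 per group (Power Analysis); a review every 5 enrolments (IX.c); 32 and 26 weeks of Entresto in Groups A and B (VIII.a); a 6-week delay in Group B (VII). Assumptions, because the documents are silent: evenly spaced entries over T weeks, alternating arms, no dropout.

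**The plan's exposure figures.** Follow-up ends at week 32. Group A: 32 − 0 = 32 weeks. Group B: 32 − 6 = 26 weeks. Both match VIII.a. Counting from the day 5 and day 47 first doses gives 31.4 and 25.4 weeks, within 3%, so the rounder figures are used. Planned total: 10 × 32 + 10 × 26 = 580 patient-weeks.

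**Triggers.** 20 / 5 = 4 reviews, at 5, 10, 15 and 20 enrolments. If data are taken up to the trigger, the newest patient has had no study drug, since dosing starts on day 5. The last patient then has 32 weeks of study left, so no dated review falls in the final 32 weeks under any accrual rate.

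**Exposure accrued at the 20th entry.** The spacing is T/19. The patient who entered j places before the last has been in the study for e = j × T/19 weeks, capped at 32, with j = 0 to 19. Exposure is e in Group A and max(e − 6, 0) in Group B. Averaging over which arm each patient is in, the total is half the sum of both.

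Example, T = 26: the spacing is 26/19 = 1.368 weeks and nobody reaches 32 weeks.

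- Group A part: ½ × 1.368 × (0 + 1 + … + 19) = ½ × 1.368 × 190 = 130.0.
- Group B part: e exceeds 6 from j = 5 on, so ½ × [1.368 × (5 + … + 19) − 15 × 6] = ½ × [1.368 × 180 − 90] = 78.2.
- Total 208.2; 208.2/580 = 36% accrued, 64% still to come.

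**Pending Group B switches.** Count patients with e < 6 and split them alternately. For T = 26 these are j = 0 to 4, five patients, so 2 or 3 are in Group B.

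| Accrual (weeks) | Patient-weeks accrued at 20th entry | Still to come | Group B switches pending, of 10 | Patients past week 32 |
|---|---|---|---|---|
| 13 | 84.7 | 85% | 4–5 | 0 |
| 26 | 208.2 | 64% | 2–3 | 0 |
| 52 | 381.5 | 34% | 1–2 | 8 |
| 104 | 473.4 | 18% | 1 | 14 |

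Which arm enrols first moves the accrued totals by less than 3 patient-weeks either way. The share still to come is 13% at 156 weeks of accrual and 10% at 208. It is half or more only if accrual takes less than about 35 weeks.

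**Earlier looks.** With 52-week accrual the four triggers see 17, 98, 237 and 382 of 580 patient-weeks, so the first sees 17/580 = 3%.

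**The case against.** The strongest reply is that safety review does not stop at the 20th enrolment, and this largely stands. Every serious and non-serious adverse event goes to the reviewer throughout, and events he deems significant go to the IRB. Staff check blood pressure at each visit and review daily PA pressures (VII.b), section V.e lists laboratory tests through week 32, nurses telephone after dose changes, and physicians are unblinded for safety. The drug is approved, used within its indication, in a 20-patient pilot. None of this is a dated aggregate look by someone independent. The other periodic check, in IX.a, has a different purpose: "The project coordinator will also review the study data on a monthly basis thereafter for accuracy".

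Four stronger readings are tempting, and the documents do not support them.

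- *No further review of these data is planned.* IX.c has the reviewer see all endpoint data, and endpoints run to week 32. That review is planned; it lacks a date.
- *The reviewer is the only independent oversight.* The IRB also receives significant events.
- *All Group B switches are still pending at the 20th enrolment.* Only Group B patients enrolled in the preceding 6 weeks can be pending, 1 to 5 of 10 in the table.
- *Nearly all late follow-up is still to come.* That holds only for fast accrual. Of the 20 × 20 = 400 patient-weeks between weeks 12 and 32, about 20% have accrued at 26 weeks of accrual, 57% at 52 and 77% at 104.

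It is also fair to say that patient-weeks weight late, stable weeks equally with titration weeks, which are planned mainly at weeks 2 and 4. At 52-week accrual, 17 of 20 patients already have at least 4 weeks on Entresto at the 20th entry. Finally, the wording in IX.c fixes no data cut-off, so a review held some time after the trigger would see more; earlier patients contribute follow-up in any case.

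**Conclusion.** The point holds as a gap in dated, aggregate, independent review, and only there. Three things follow from the text without any assumption: the dated cumulative reviews are triggered by enrolment, they carry no minimum follow-up or cut-off, and none is dated in the last 32 calendar weeks, which contain the last patient's full 32 or 26 weeks of Entresto. For the same reason the p < 0.01 harm guideline has no dated look in that period.

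The amount of exposure affected is not fixed by the documents. It ranges from about 85% of planned patient-weeks (13-week accrual) to about 18% (104-week accrual), given even accrual, alternating arms and no dropout. Given the continuous event review and per-patient monitoring, this is something the sponsor should correct rather than a flaw that undermines the trial.

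**What to change.** In section IX.c, replace the enrolment trigger with three elements:

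- a cumulative review after every 5 patients complete the week 12 visit, by which time those patients are scheduled to have had about 12 weeks (Group A) or 6 weeks (Group B) on Entresto;
- a fixed calendar interval, for example every 3 months, until the last patient's week 32 visit;
- a final review at that visit.

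State the data cut-off for each review, and say at which of them the existing harm guideline is applied. The week 12 and 3-month figures are examples; what matters is that the trigger counts follow-up and that reviews run to the end.

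The cost is amended wording and a few more reviews by the same reviewer on data already collected. No treatment, visit or endpoint changes. One drawback is that, with slow accrual, the first review triggered by follow-up comes later than the fifth enrolment; the calendar review covers that.

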### *Other Endpoints:*

- *Death*
- *All-cause re-hospitalization*
- *Need to progress to advanced therapies (i.e. start home inotropes, place a ventricular assist device or list for cardiac transplantation)*
- *Unscheduled visits for IV loop diuretics*
- *Other interventions (i.e. nutrition referrals)*

*\*Will be 3 comparisons:*

- 1) 6 weeks of Entresto vs 6 weeks of continued ACEI/ARB (Group A compared to B at 6 weeks)
- 2) Baseline on ACEI/ARB compared to 6 weeks on Entresto (Groups A and B combined)
- 3) 12 weeks on Entresto compared to 32 weeks on Entresto in longitudinal study (all pts)

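### The only trial-level stopping rule (p<0.01 for harm) cannot be operated as written, and a between-arm comparison of patients with an event cannot reach it at the first review

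*Combined protocol and SAP*

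**What the plan says.** Section IX.c (Outcome Monitoring) sets the rule in one sentence: "The study will have a pre-specified stopping guideline of" p<0.01 "for harm on any safety outcomes". On timing it says "He will review all clinical and safety data after every 5 patients have been enrolled", which with 20 patients means reviews at 5, 10, 15 and 20. On the reviewer it says "He will be blinded to the study group assignment and will review this data in a de-identified fashion". Section IX.b adds that "we will not have a formal Data Safety Monitoring Board".

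Other safeguards are in place:
- Treating physicians know the assignment (Section II, Study Design).
- For a patient with an adverse reaction "that cannot be ameliorated with dose reduction or adjustment, the medication will be stopped" (Section VII.b).
- Potential adverse events go to the independent reviewer as soon as possible when they occur (IX.c).
- Section IX.d says "angioedema is an event of special interest, and all angioedema-like events will be submitted for independent review", and it sends event reports to the manufacturer together with the randomization codes.

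Candidate safety outcomes appear in several places. Other Endpoints lists death, "All-cause re-hospitalization", advanced therapies and unscheduled visits for IV diuretics. Section VII.b names hypotension, hyperkalemia and renal dysfunction as the main side effects. None of these is tied to the stopping rule.

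The laboratory schedule is given twice and differently. The visit table in V.a places safety labs at week 2 for Group A only and at week 8 for Group B only, plus after dose changes. Section V.e and the data collection form list weeks 2, 6, 8, 12, 24 and 32 with no split by group.

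**The concern.** A stopping rule needs an outcome, a comparison, a period, and someone who can make the comparison and act on it. Here each is missing or open.

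- **Outcome.** Any safety outcome qualifies, and the three main side effects have no event threshold.
- **Test.** None is named, nor whether it is one- or two-sided. The t-test/Wilcoxon choice in Statistical Analysis is written for other endpoints, and that section contains no safety analysis.
- **Period.** Group B moves to Entresto after week 6 (Section IV.b), so data after that no longer contrast the two treatments.
- **Person.** The reviewer cannot see group. Those who can (treating physicians, and the manufacturer through the codes) are given neither the comparison nor the decision.

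So the rule is called pre-specified, yet whether it fires depends on choices left until data are in hand. If the V.a table is the laboratory schedule in force, potassium and creatinine are also collected unevenly during the only weeks when the arms differ.

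**Working it through.** The plan gives no operating characteristic for the rule, so there is no figure of its own to reproduce.

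**Inputs from the protocol.** 20 patients, 10 per group (Power Analysis); reviews after every 5 enrolled and threshold p<0.01 (IX.c); treatment contrast ends at week 6 (IV.b).

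**Assumptions.** The documents give no rates for hypotension, hyperkalemia or renal dysfunction, so three pairs of true risks are tried: 40%, 50% and 70% on Entresto, each against 10%. The four reviews are taken at 3 v 2, 5 v 5, 8 v 7 and 10 v 10, with complete data on everyone enrolled.

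**First review, 5 enrolled.** The most extreme result is an event in every patient of one arm and none in the other.
- Fisher, 3 v 2 split: 1/C(5,2) = 1/10 = 0.10. A 4 v 1 split gives 1/5 = 0.20.
- Uncorrected chi-square: the statistic cannot exceed N = 5, so p = 0.025.

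Neither is below 0.01.

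**Later reviews: smallest excess that fires with no control events.**
- 5 v 5, Fisher: 5 v 0, since 1/C(10,5) = 1/252 = 0.0040 one-sided and 0.0079 two-sided.
- 5 v 5, chi-square: 4 v 0.
- 10 v 10, two-sided Fisher: 7 v 0. One tail is C(10,7)/C(20,7) = 120/77,520 = 0.00155, doubled 0.0031. At 6 v 0, p = 0.0108, which misses.
- 10 v 10, one-sided Fisher: 6 v 0, C(10,6)/C(20,6) = 210/38,760 = 0.0054.
- 10 v 10, chi-square: 5 v 0, 20 × (5×10 − 5×0)² / (5×15×10×10) = 6.67, p = 0.0098.

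**Chance of firing toward harm.** The final look is by exact enumeration, the four looks by 400,000 simulations.

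| True risks | Looks | Two-sided Fisher | One-sided Fisher | Chi-square |
|---|---|---|---|---|
| 40% v 10% | final only | 2.4% | 8.0% | 15% |
| 40% v 10% | all four | 3.6% | 8.4% | 17% |
| 50% v 10% | all four | 11% | 21% | 33% |
| 70% v 10% | all four | 45% | 61% | 70% |

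Between the least and most permissive test the ratio is 17/3.6, about 4.7, at 40% v 10%; 33/11, about 3, at 50% v 10%; and 70/45, about 1.6, at 70% v 10%.

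**Sensitivity to the split.** Section IV.b describes no blocking, so unequal groups are plausible. At 40% v 10%, final look, two-sided Fisher gives 2.4% at 10 v 10 (needs 7 v 0), 4.5% at 9 Entresto v 10 (needs 6 v 0) and 9.4% at 9 v 11 (needs 5 v 0). The 1:1 figures are therefore not upper bounds. At 9 v 11 the three tests give 9.4%, 9.4% and 12.7%, so there the choice of test matters less.

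**Other readings of the rule.** A two-sided t-test on a continuous safety measure fires over four reviews 35% of the time for a true 1-SD harm and 94% for 2 SD. Its false-stop chance toward harm is 1.6% per measure. A single-arm test of one angioedema case among 5 patients against the 0.2% quoted in VII.b gives 1 − 0.998^5 = 0.00996, just under 0.01.

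**The case against.** The strongest reply is proportion. This is a 20-patient pilot of an approved drug used on label, physicians are unblinded, an individual's drug is stopped when a reaction cannot be managed, and an outside cardiologist sees events as they happen. All of that stands. A reader might infer that the trial has no safety oversight, or that serious harm would go unseen until the fifth patient; the documents support neither. What those safeguards lack is a statement of when the trial itself should pause, and the protocol chose to promise one.

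Second, a reader might infer that the rule cannot fire at the first review on any reading. It could, through a continuous measure or a single-arm test, since IX.c does not say the comparison is between arms. The limit applies only to between-arm comparison of patients with an event. That the answer turns on which reading is taken is itself the difficulty.

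Third, it is tempting to say that a large harm is usually missed whichever test is used, or that the test alone changes the firing chance more than fourfold. The first fails at 70% v 10%, where two of the three tests fire more often than not. The second holds only at 40% v 10% with exact 1:1 splits.

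Fourth, the V.a table is evidently not the full laboratory list: V.e collects baseline potassium and creatinine, which the table's safety-lab row does not show. The documents therefore do not establish that Group B lacks potassium and creatinine on ACEi/ARB. They show two schedules that disagree. Only if V.a governs might a Group B patient whose dose never changes have no such values during weeks 0-6.

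**Conclusion.** The point holds. The only trial-level stopping rule cannot be carried out as written, because no specific outcome, test, sidedness or period is set and nobody is assigned the comparison or the decision. This rests on the text alone.

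The arithmetic adds that, read as a between-arm comparison of patients with an event, the rule is unattainable at 5 enrolled and needs a very lopsided result at 10 v 10. It is weak at assumed risks of 40% v 10% (about 4% to 17% by test) and 50% v 10% (11% to 33%), and moderate at 70% v 10% (45% to 70%). Those percentages depend on assumed rates, 1:1 splits and complete data at each review. Incomplete follow-up and unequal splits would change them, and some unequal splits raise them.

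The effect is on safety monitoring. The primary efficacy comparison is unaffected, and the existing patient-level safeguards limit the consequence. The change should be made, but the omission does not leave patients unmonitored.

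**What to change.** 1. In IX.c, stop relying on p<0.01 for event counts. Use clinical pause-and-review triggers: at minimum, any angioedema or drug-related death. If the clinicians want count thresholds for hypotension, hyperkalemia or renal dysfunction, they should set the event definitions, the counts and an exposure window, for example the first 6 weeks on Entresto. Name who decides on a pause.
2. Limit any between-arm safety comparison to weeks 0-6.
3. Name an existing unblinded staff member to give the independent reviewer safety counts by arm at each of the four reviews, without patient identifiers and separate from the PA-pressure data reviewed blinded.
4. Correct the V.a table to match V.e and the data collection form, so both groups have potassium and creatinine at weeks 2 and 6.
5. Report week-6 differences, Group A v Group B, with 95% confidence intervals for blood pressure, potassium and creatinine, as estimates and not as tests.

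**Cost.** One rewritten paragraph, one table row and a short count table four times. If V.e already governs, no new tests are needed. If V.a does, at most 10 (Group A, week 6) + 20 (Group B, weeks 2 and 6) = 30 added panels, fewer where dose-change labs already fall at those visits. The reviewer will see safety counts by arm. An unnecessary pause is possible: at the 0.2% angioedema rate in VII.b, 1 − 0.998^20 = 0.039, about 4% over 20 patients. Any count thresholds the clinicians add would raise that.
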